#### **10.3.3 Remote Monitoring Visits/Review**

DCC monitors and data managers will also perform remote review of source documentation, CRFs and investigational product accountability to achieve the goals described in section 10.3.2. Remote review involves a range of data management procedures (queries, edit checks, review of missing data, etc.), as well as more traditional monitoring procedures conducted remotely through the exchange and review of source documentation and CRFs. DCC monitors will request access to source documentation and CRFs through the following methods:

1. Remote review of electronic medical records
2. Site upload of source documentation and CRFs to a secure portal hosted and managed by the DCC.
3. Site upload of source documentation and CRFs to a secure portal hosted and managed by the site.

DCC monitors will contact site staff as early as possible in the course of a trial to arrange remote access to source documentation and CRFs. Sites are required to comply with DCC requests for remote access.

Additionally, the DCC will conduct remote reviews of investigational product accountability and storage conditions after an initial on-site visit to each site's pharmacy. DCC monitors will request accountability records and temperature logs from CSS coordinators or study pharmacists in order to complete these remote reviews.

#### **10.3.4 Laboratory Data Flow**

Safety Monitoring Labs: The DCC will provide laboratories with online forms and/or electronic data exchange mechanisms - depending on their capabilities and needs - to enter, update and obtain relevant data. When a blood sample has been obtained, the clinical study site study coordinator will send the sample (participant ID, site ID, and protocol ID numbers will be used) to the University of Rochester Central Laboratory. The laboratory will electronically communicate the test results to the respective clinical study sites in a secure manner. The laboratory will also transfer test results electronically to the DCC.

### **10.4 Adverse Experience Reporting**

The adverse event (AE) definitions and reporting procedures provided in this protocol comply with all applicable United States Food and Drug Administration (FDA) regulations and International Conference on Harmonization (ICH) guidelines. The Site Investigator will carefully monitor each subject throughout the study for possible adverse events. All AEs will be documented on CRFs designed specifically for this purpose. It is important to report all AEs, especially those that result in permanent discontinuation of the investigational product being studied, whether serious or non-serious.

Subjects will be monitored for AEs from the time they sign consent until the final Study visit. If an AE is ongoing or discovered at a subject's final Study visit, the AE will be followed until resolution, or for a minimum of 30 days, whichever comes first. Resolution means that the subject has returned to status at enrollment. If the AE is still ongoing after 30 days, it will be resolved with sequelae. All AEs monitored past the final visit can be followed via telephone – a repeat Termination/Final Follow-up visit does not need to occur.

All SAEs must be followed until resolution throughout the trial. SAEs that are discovered less than 60 days prior to the subject's final Study visit will be followed until resolution or for a minimum of 60 days, whichever comes first, even if it is past the final visit. If a new SAE is discovered at the subject's final Study visit, it must be followed until resolution, or for a minimum of 60 days, whichever comes first. If the SAE is still ongoing after 60 days, it will be resolved with sequelae. All SAEs monitored past the final visit can be followed via telephone – a repeat Termination/Final Follow-up visit does not need to occur.

Each clinical study site's Principal Investigator and research team are responsible for identifying adverse events and reporting them through the DCC Online Adverse Event Reporting System. Investigators are also responsible for complying with NeuroNEXT CIRB's reporting requirements for all safety reports. Copies of each report and documentation of IRB notification and receipt will be kept in the investigator's study file.

An adverse event is defined as: "...an unfavorable and unintended sign, symptom, or disease associated with a participant's participation in this research trial."

Serious adverse events include those events that: "result in death; are life-threatening; require inpatient hospitalization or prolongation of existing hospitalization; create persistent or significant disability/incapacity, or a congenital anomaly/birth defects."

Unexpected adverse event is defined as any adverse experience...the specificity or severity of which is not consistent with the risks described in the protocol.

Expected adverse events are those that are known to be associated with or have the potential to arise as a consequence of participation in the study.

### ***On-line Adverse Event Reporting System***

Upon entry of a serious adverse event by a site investigator, the DCC Online Adverse Event Reporting System will immediately notify the Independent Medical Monitor (IMM).

- Within **24 hours** (of learning of the event), investigators must report any Serious Adverse Event (SAE). Investigators should report all other AEs within **5 working days/7 calendar days** (of learning of the event).

Serious adverse events: The site investigator determines causality (definitely not related, probably not related, possibly related, probably related, definitely related) of the adverse event. The IMM will review the SAE report. The IMM may request further information if necessary. The Online Adverse Event Reporting System maintains audit trails and stores data (and data updated) and communication related to any adverse event in the study. The IMM may determine that the Serious Adverse Event requires expedited reporting to the FDA. The DCC will prepare a MedWatch safety report for submission to the FDA. If warranted, the IMM will notify the DSMB chair. The DSMB may suggest changes to the protocol or consent form to the Study Chair as a consequence of adverse events.

Non-serious adverse events: Non-serious adverse events that are reported to or observed by the investigator or a member of his research team will be submitted to the DCC in a timely fashion (within 5 working days). The events will be presented in tabular form and given to the IMM on a quarterly basis or as requested. Local site investigators are also required to fulfill all reporting requirements of their local institutions.

The DCC will prepare aggregate reports of all adverse events (serious/not serious, expected/unexpected and relationship to study drug) for the IMM and the DSMB on a quarterly basis or as requested. In addition, all adverse events will be coded using the MedDRA system. A separate report detailing protocol compliance will also be available from the DCC for DSMB and/or site review monthly or as requested. The research team will then evaluate whether the protocol or informed consent document requires revision based on the reports.

#### **10.4.1 Definitions of Adverse Events, Suspected Adverse Drug Reactions & Serious Adverse Events**

##### **10.4.1.1 Adverse Event and Suspected Adverse Drug Reactions**

An adverse event (AE) is any unfavorable and unintended sign (including a clinically significant abnormal laboratory finding, for example), symptom, or disease temporally associated with a

study, use of a drug product or device whether or not considered related to the drug product or device.

Adverse drug reactions (ADR) are all noxious and unintended responses to a medicinal product related to any dose. The phrase “responses to a medicinal product” means that a causal relationship between a medicinal product and an adverse event is at least a reasonable possibility, i.e., the relationship cannot be ruled out. Therefore, a subset of AEs can be classified as suspected ADRs, if there is a causal relationship to the medicinal product.

Examples of adverse events include: new conditions, worsening of pre-existing conditions, clinically significant abnormal physical examination signs (i.e. skin rash, peripheral edema, etc.), or clinically significant abnormal test results (i.e. lab values or vital signs), with the exception of outcome measure results, which are not being recorded as adverse events in this trial (they are being collected, but analyzed separately). Stable chronic conditions (i.e., diabetes, arthritis) that are present prior to the start of the study and do not worsen during the trial are NOT considered adverse events. Chronic conditions that occur more frequently (for intermittent conditions) or with greater severity, would be considered as worsened and therefore would be recorded as adverse events.

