Adverse events seen in the prior adolescent and adult placebo-controlled studies of AFQ056 in FXS more frequently in the group treated with AFQ056 than with placebo include the following list arranged in alphabetical order. No side effect exceeded a frequency of 20%, even at the highest doses of AFQ056 (see section 2.2 above for exact frequencies). In the Pediatric PK study, side effects all fell into the below categories, with vomiting and insomnia being the most frequent side effects. These were typically short-lived occurring in the first day or two of dosing and seemingly related to advancing to the full dose right from the outset of doing rather than titrating the dose up over time. This was evident in that vomiting after the initial dose was seen in 50% of the 5-11 year old cohort studied first all of whom were dosed from the outset at the full dose, but not seen in the 3-4 year old cohort after dosing was advanced over the course of a day (half dose for one day, followed by the full dose).

- Abdominal pain
- Agitation
- Aggression
- Anxiety
- Decreased appetite
- Diarrhea
- Dizziness
- Fatigue
- Headache
- Insomnia
- Irritability
- Nausea
- Pyrexia
- Self-injurious behavior
- Vomiting

Although not seen in prior trials in humans with FXS, including after AFQ056 exposure for over two years in the open-label extension studies with adults and adolescents (2278 and 2279), learning and memory impairment have been noted in preclinical testing of AFQ056. Learning was, however, enhanced in preclinical testing in the FXS mouse model, presumably due to the AFQ056 targeting the abnormal signaling pathway in the FXS mouse. Risk of learning and memory impairment will be monitored closely using assessments that are being administered as part of the protocol. Raw scores on the MSEL and VABS-II assessments will be monitored at the sites to assess global developmental functioning. If there is a decrease in raw scores on both measures by 10% incrementally at two consecutive visits where both assessments are administered (e.g. 10% decrease from screening to baseline, baseline to month 2, month 2 to month 8, or month 8 to month 16 as described in the schedule of assessments), subject data will be reviewed by the Medical Monitor and it will be decided if the subject should be withdrawn from the study. If there is decrement in these scores without any obvious alternative cause the participant will be withdrawn from the study.

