## 9.7 Safety Analysis

Secondary analyses to examine long-term safety of AFQ056 in this cohort of young children with FXS will be done as follows. Frequencies of adverse events occurring throughout the entire treatment period (both clinical and laboratory) will be tabulated and compared between the active drug and placebo groups during the placebo-controlled period of the study (8 months) and compared across the entire study duration divided based on treatment-assignment at the time of the AE. **Low frequency AEs occurring in less than 5% of the cohort and those that are not different between the drug and placebo groups by visual inspection will not be analyzed further.** Higher frequency events for which statistical comparison would be possible and that appear to be occurring at different frequencies between the drug and placebo groups for either set of comparator groups will be formally compared statistically using a chi-squared analysis. Longitudinal analyses will be done for AEs occurring more frequently in the AFQ056-treated group to determine if there is an increase over time of treatment in these AEs.

[figure not shown]
AFQ056 for Language Learning in Children with FXS

Version v15

Version date 02/03/2021

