**Adverse events are generally detected in two ways:**

**Clinical → symptoms reported by the subject or signs detected on examination.**

**Ancillary Tests → abnormalities of vital signs, laboratory tests, and other diagnostic procedures (other than the outcome measures: the results of which are not being captured as AEs).**

If discernible at the time of completing the AE, a specific disease or syndrome rather than individual associated signs and symptoms should be identified by the Site Investigator and recorded on the AE CRF. However, if an observed or reported sign, symptom, or clinically significant laboratory anomaly is not considered by the Site Investigator to be a component of a specific disease or syndrome, then it should be recorded as a separate AE CRF. Clinically significant laboratory abnormalities, such as those that require intervention, are those that are identified as such by the Site Investigator.

An unexpected adverse event is any adverse event, the specificity or severity of which is not consistent with the current Investigators Brochure or package insert or described in the protocol. An unexpected, suspected adverse drug reaction is any unexpected adverse event that, in the opinion of the Site Investigator or Sponsor, there is a reasonable possibility that the investigational product caused the event.

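### Skill loss detected only by MSEL and Vineland scores, which Section 7 monitors as a named risk, is not counted by arm in any planned safety analysis

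*Combined protocol and SAP*

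**What the plan says.** Section 7 reports that learning and memory impairment was seen in preclinical testing, though not in earlier human trials in fragile X. It commits to follow-up: "Risk of learning and memory impairment will be monitored closely using assessments that are being administered as part of the protocol". Sites watch the raw scores of the MSEL and of an instrument called VABS-II. The trigger reads "If there is a decrease in raw scores on both measures by 10% incrementally at two consecutive visits where both assessments are administered", after which the Medical Monitor reviews the child's data. The section then adds: "If there is decrement in these scores without any obvious alternative cause the participant will be withdrawn from the study".

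Section 9.5.2 lists the MSEL and the Vineland-3 among the key secondary outcomes.

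Section 10.4.1.1 lists what counts as an adverse event, "with the exception of outcome measure results, which are not being recorded as adverse events in this trial", and notes of those results that "they are being collected, but analyzed separately". The same section repeats the exclusion where it describes how events are detected from ancillary tests: "other than the outcome measures: the results of which are not being captured as AEs". Neither statement makes an exception for the Section 7 rule.

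Section 9.7 sets out the safety analysis: "Frequencies of adverse events occurring throughout the entire treatment period (both clinical and laboratory) will be tabulated" and compared between arms. Events in fewer than 5% of the cohort are not analysed beyond that tabulation. Section 9.5.3 gives the safety endpoints as adverse events, clinically significant laboratory values and tolerability, where failure means having to stop after reduction to 12.5 mg.

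**The concern.** The protocol has a detector for a risk it names itself, but no planned readout from that detector by treatment arm. The children are 3 to 6 years old, and Section 6.3.9 accepts that they will not be able to report all, or perhaps any, side effects. Repeated standardised scores are therefore a more systematic check for lost skills than spontaneous report. If some children on AFQ056 lost skills on both instruments and others did not, the trial would hold the data to show it. The planned safety analysis would not ask the question.

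At stake is what the final report can say about the risk. A mean slope can look acceptable while a few children decline, and an adverse-event table with no entry for score-defined decline says nothing either way.

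**Working it through.** The plan states no figure on this point, so there is none to reproduce. The check sets the sections side by side and then asks how an uncommon event would fare under the rules in 9.7.

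**Step 1: does a score-defined decline reach any safety count?**

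| Link | Where | Result |
|---|---|---|
| Trigger uses MSEL and Vineland raw scores | Section 7 | Both are outcome measures (9.5.2) |
| Outcome-measure results | 10.4.1.1, stated twice | Not recorded as adverse events |
| Between-arm safety comparison | 9.7 | Adverse events, clinical and laboratory |
| Tolerability | 9.5.3 | Counts stopping after reduction to 12.5 mg, not stopping on scores |
| Reason for withdrawal | 4.3 | Recorded on the completion/termination form; no by-arm comparison specified |
| MSEL and Vineland analysis | 9.6.1, 9.6.2 | Mean rate of change, as efficacy |

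A child withdrawn solely on the score rule adds no adverse event and no tolerability failure.

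**Step 2: when can the trigger occur in the controlled period?** In Table 7 the MSEL is given at screening, baseline, month 2 and month 8, and the Vineland at all of these visits. Only two intervals between joint visits follow randomisation: baseline to month 2, and month 2 to month 8. If the rule needs one interval with a 10% fall, it can be met at month 2 or month 8. If it needs two successive falls, a trigger resting wholly on post-randomisation change cannot occur before month 8.

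**Step 3: would recording the decline as an adverse event be enough?** With 100 randomised (Section 9.8), 5% of the cohort is 0.05 × 100 = 5 children. Fewer than 5 events would be tabulated but not analysed further.

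Hypothetical: 4 of 50 on AFQ056 and 0 of 50 on placebo.
- Risk difference: 4/50 − 0/50 = 0.08, or 8 points. Fisher exact two-sided p = 0.117.
- Share of cohort: 4/100 = 4%, below the 5% line.
- Exact 95% intervals: 2.2% to 19.2% for 4/50. For 0/50 the upper limit is 1 − 0.025^(1/50) = 7.1%.

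The next table uses assumed rates (the documents give none), 50 children per arm and independent binomial counts. The filter column is P(X + Y < 5). Power is for Fisher's exact test at an assumed two-sided 0.05, summed over all pairs of counts.

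| Placebo rate | AFQ056 rate | Chance of fewer than 5 events | Power |
|---|---|---|---|
| 0% | 4% | 95% | 1% |
| 0% | 8% | 63% | 21% |
| 2% | 10% | 27% | 19% |
| 2% | 20% | 1% | 78% |

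With no placebo events, 5 v 0 gives p = 0.056 and 6 v 0 gives p = 0.027. At low rates the event would usually be filtered out, and a formal test has little power. The useful output is the count with an exact interval, and it needs its own line outside the filter.

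**The case against.** The best reply is that the risk is visible in other ways, and much of that stands.

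- The exclusion covers test results, not clinical regression. Parents are asked at each visit about changes in the child, and Section 6.3.14 makes clinically significant worsening an adverse event. The Vineland is itself a parent interview, so a parent whose answers produced a 10% fall may well report the loss as well. A reader might infer that the safety tables are blind to all learning loss. The documents do not support that; only loss detected solely by scores is excluded.
- The scores are analysed separately, the Medical Monitor reviews each trigger, the termination form carries the reason, and Section 9.9 has the DSMB monitor endpoints as well as adverse events. This gives partial visibility, but none of it is specified as a count of decliners by arm.
- A formal analysis plan is still to be written (opening of Section 9, and 9.6.2), so such a count could yet appear. That is a reason to ask for it.

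A reader might also infer that withdrawn decliners take the worst trajectories out of the primary slope model and so flatter the drug. The documents do not show this. A trigger at month 8 loses no controlled-period data. After a month 2 trigger the scores already observed stay in the likelihood-based model, and a child still on drug has the month 16 battery at termination. The primary model uses the weighted communication score, and nothing ties it to MSEL and Vineland declines.

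Nor does Section 7 withdraw every child whose scores fall: it refers to a 10% fall on both measures, Medical Monitor review and the absence of an obvious alternative cause.

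**Conclusion.** The point holds in a limited form. A decline found only by the Section 7 scores, or a withdrawal based on it, is not counted by arm in any safety analysis the protocol sets out. This rests on reading 10.4.1.1 as written and on 9.5.3 and 9.7 being the whole of the planned safety analysis.

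Its size cannot be stated, because the documents give no rate of decline. The 4 v 0 case is hypothetical. It shows only that an 8-point difference could go without a required by-arm display, and that adverse-event recording alone would leave it under the 5% filter. The documents do not show that harm is hidden, or that efficacy is biased by these withdrawals. This is a cheap improvement to the safety reporting, not a defect in the trial's main comparison.

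**What to change.** Add to 9.7 a pre-specified table by randomised arm for the 8-month controlled period, exempt from the 5% filter, with exact confidence intervals, giving:

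- (a) the number of children with a raw-score fall of 10% or more on both measures between consecutive joint MSEL/Vineland visits;
- (b) the number withdrawn under Section 7.

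Compute (a) centrally from the raw scores already in the case report forms, and cross-reference the table from 10.4.1.1 as the exception to the outcome-measure exclusion.

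The criterion must first be computable. Reconcile VABS-II in Section 7 with the Vineland-3 used everywhere else. State which raw scores apply: the forms hold MSEL subscale and Vineland domain raw scores, but the Vineland composite only as a standard score (6.3.9, 6.3.13). Reconcile the two readings of the consecutive-visit wording. The definition in (a) is for reporting only and leaves the clinical withdrawal rule unchanged.

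The cost is this clarification, one derivation and one extra table, with no new data collection. The downside is a low-powered comparison, so it should be read as counts and intervals, not as a test.

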**Adverse events are generally detected in two ways:**

**Clinical → symptoms reported by the subject or signs detected on examination.**

**Ancillary Tests → abnormalities of vital signs, laboratory tests, and other diagnostic procedures (other than the outcome measures: the results of which are not being captured as AEs).**

If discernible at the time of completing the AE, a specific disease or syndrome rather than individual associated signs and symptoms should be identified by the Site Investigator and recorded on the AE CRF. However, if an observed or reported sign, symptom, or clinically significant laboratory anomaly is not considered by the Site Investigator to be a component of a specific disease or syndrome, then it should be recorded as a separate AE CRF. Clinically significant laboratory abnormalities, such as those that require intervention, are those that are identified as such by the Site Investigator.

An unexpected adverse event is any adverse event, the specificity or severity of which is not consistent with the current Investigators Brochure or package insert or described in the protocol. An unexpected, suspected adverse drug reaction is any unexpected adverse event that, in the opinion of the Site Investigator or Sponsor, there is a reasonable possibility that the investigational product caused the event.

